1. PROTOCOL SUMMARY

Title	A PHASE I/II STUDY OF ACTIVE IMMUNOTHERAPY WITH Ad5 [E1-, E2b-]-CEA(6D) VACCINE (ETBX-011) IN PATIENTS WITH ADVANCED OR METASTATIC MALIGNANCIES EXPRESSING CEA
Objectives	
a) The primary objective of this protocol is to determine the safety of immunization with Ad5 [E1-, E2B-]-CEA(6D), in patients with advanced or metastatic CEA-expressing malignancies.
 
b) The secondary objectives are to evaluate CEA-specific immune responses to the immunizations and to obtain preliminary data on clinical response rate.

Major Inclusion/ Exclusion Criteria	
Patients with a histologically confirmed diagnosis of metastatic malignancy who were previously treated with standard therapy known to have a possible survival benefit or refused such therapy. The tumor must express CEA as defined by any of the following: immunohistochemical staining, a CEA level in the peripheral blood greater than 5 ng/dL, or a tumor known to be universally CEA positive (i.e. colon and rectal cancer). Patients will not be treated until 4 or more weeks after any prior chemotherapy or radiation therapy, but may be receiving non-cytotoxic targeted therapy (bevacizumab, cetuximab, trastuzumab, erlotinib, or gefitinib) or hormonal therapy. They must not have a history of autoimmune disease, serious intercurrent chronic or acute illness, active hepatitis, serologic evidence for HIV, or be receiving steroid or immunosuppressive therapy. All patients must be >18 years old and have an ECOG Performance Status of 0 or 1. Pregnant women and nursing mothers are excluded.

Study Design	
Phase I/II study with three dosage levels of Ad5 [E1-, E2B-]-CEA(6D) vaccine (phase I component), and the maximally tolerated dose of Ad5 [E1-, E2B-]-CEA(6D) vaccine (phase II component). The study drug is Ad5 [E1-, E2B-]-CEA(6D) given by subcutaneous (SQ) injection every 3 weeks for 3 immunizations. The following procedures will occur:
 
 1) Peripheral blood draw of 90 mL for immune analysis 2) Cohort 1: Three patients will receive Ad5 [E1-, E2B-]-CEA(6D) at a dose of 1×10^9 particles SQ in 0.5 mL every 3 weeks for 3 immunizations. Assessment of dose-limiting toxicities (DLT) for dose escalation will be made after all patients in this cohort have had a study visit at least 3 weeks after receiving their first dose of vaccine. If there are no DLT, defined as any Grade 2, 3 or 4 immediate hypersensitivity reactions or neurological toxicity, other Grade 3 or 4 allergic or major organ toxicity, or Grade 4 fever, that may possibly be associated with the immunization), then patients may

	
begin enrolling into cohort 2. If there is 1 DLT, then an additional 3 patients will be enrolled at this dosage level. Assessment of DLT for dose escalation will be made after the 3 additional patients have had a study visit at least 3 weeks after receiving their first dose of vaccine. If none of these latter 3 patients have DLT (i.e., 1 DLT in the 6 total patients), then patients may begin enrolling into cohort 2.
 
3) Cohort 2: Three patients will receive Ad5 [E1-, E2B-]-CEA(6D) at a dose of 1×10^{10} particles SQ in 0.5 mL every 3 weeks for 3 immunizations. Assessment of DLT for dose escalation will be made after all patients in this cohort have had a study visit at least 3 weeks after receiving their first dose of vaccine. If there are no DLT, then patients may begin enrolling into cohort 3. If there is 1 DLT then an additional 3 patients will be enrolled at this dosage level. Assessment of DLT for dose escalation will be made after the 3 additional patients have had a study visit at least 3 weeks after receiving their first dose of vaccine. If none of these latter 3 patients have DLT, then patients may begin enrolling into cohort 3.
 
4) Cohort 3: Six patients will receive Ad5 [E1-, E2B-]-CEA(6D) at a dose of 1×10^{11} particles SQ in 0.7 mL every 3 weeks for 3 immunizations. Assessment of DLT for proceeding to phase II enrollment will be made after all patients in this cohort have had a study visit at least 3 weeks after receiving their first dose of vaccine. If there is 0 or 1 DLT, then patients may begin enrolling into the phase II portion of the study.
 
5) Phase II cohort: An additional 12 patients will receive Ad5 [E1-, E2B-]-CEA(6D) at the maximally tolerated dose every 3 weeks for 3 immunizations.
 
6) Patients will have 90 mL peripheral blood drawn prior to each immunization and at Week 9 to determine whether there is an effect on the immune response at specific time points during the study and/or after a specific number of immunizations.
 
7) Time to progression will be measured using CT scans performed as per standard of care (approximately 3 month intervals).

Risks/toxicities	Potential risks associated with the vaccine include anaphylaxis, fever, skin reaction, autoimmunity (colitis), and hepatic insufficiency.
Number of Patients	Planned: 24 evaluable patients (plus up to 12 replacements); may require 30-42 patients if DLT occur.
Duration of Study	6 months after the last patient is enrolled; approximately 2 years total
Criteria for Evaluation	Toxicity will be assessed using CTC toxicity criteria. CEA-specific immune response will be measured by ELISpot. Time to recurrence will be determined by RECIST criteria.
Statistical Analysis	Safety: We will evaluate safety in each cohort at least 3 weeks after the last patient in the previous cohort has received their first injection. A dosing scheme will be considered safe if <33% of patients treated at a

[REDACTED]

[REDACTED]

[REDACTED]

[REDACTED]

[REDACTED]

[REDACTED]

[REDACTED]

[REDACTED]

[REDACTED]

[REDACTED]

[REDACTED]

- [REDACTED]

[figure not shown]
[figure not shown]
[figure not shown]
[REDACTED]

[figure not shown]
[REDACTED]

[REDACTED]

--	--

A
		

4. PATIENT SELECTION

4.1. Criteria for Patient Eligibility

- 4.1.1. Histologically confirmed diagnosis of metastatic malignancy due to a tumor expressing CEA. Because this is a safety and immunogenicity study, patients are NOT required to have measurable or evaluable disease by Response Evaluation Criteria in Solid Tumors (RECIST).
- 4.1.2. The tumor must express CEA as defined by any of the following: immunohistochemical staining (at least 50% of the tumor with at least moderate intensity of staining), a CEA level in the peripheral blood greater than 5.0 ng/mL at any time prior to enrollment, or a tumor known to be universally CEA positive (i.e. colon and rectal cancer.)
- 4.1.3. Patients must have received treatment with standard therapy known to have a possible overall survival benefit or refused such therapy.

For the following common cancers, the following eligibility criteria apply:

- Colorectal cancer: Must have received and progressed through at least one line of palliative chemotherapy consisting of one of the following regimens:

- Palliative chemotherapy for metastatic colorectal cancer with 5-fluorouracil (or capecitabine) and oxaliplatin.
- Palliative chemotherapy for metastatic colorectal cancer with 5-fluorouracil (or capecitabine) and irinotecan.
- Palliative chemotherapy regimen for metastatic colorectal cancer that includes bevacizumab.
- Colorectal cancer patients currently receiving palliative single-agent bevacizumab or cetuximab will be eligible for this trial and may continue these therapies concomitant with study treatment (if they have been on these therapies for at least 3 months).
- Breast cancer: Must have received and progressed through at least one line of chemotherapy for metastatic breast cancer consisting of one of the following regimens:
 - Palliative anthracycline- or taxane-based chemotherapy
 - Patients with tumors that over express HER2 (IHC 3+ or FISH+) must have received and progressed through at least one line of palliative therapy that combines trastuzumab with chemotherapy.
 - Breast cancer patients currently receiving palliative endocrine therapy or single-agent trastuzumab will be eligible for this trial and may continue these therapies concomitant with study treatment (if they have been on these therapies for at least 3 months).
- Lung cancer: Must have received and progressed through chemotherapy for metastatic disease consisting of one of the following regimens:
 - Palliative platinum-based (cisplatin or carboplatin) chemotherapy if the patient has not received chemotherapy previously.
 - Palliative taxane-based (docetaxel or paclitaxel) or vinorelbine chemotherapy if the patient has received chemotherapy previously.
 - Lung cancer patients currently receiving palliative single-agent erlotinib or gefitinib will be eligible for this trial and may continue these therapies concomitant with study treatment (if they have been on these therapies for at least 3 months).
- Pancreatic cancer: Must have received and progressed through chemotherapy including gemcitabine.
 - Pancreatic cancer patients currently receiving palliative single-agent erlotinib will be eligible for this trial and may continue this therapy concomitant with study treatment (if they have been on this therapies for at least 3 months).
- For other malignancies, if a first line therapy with survival or palliative benefit exists, it should have been administered and there should have been progressive disease.

- Patients who have received and progressed through first-line palliative chemotherapy must be advised regarding second-line therapy before being enrolled on this investigational study.
- 4.1.4. ECOG 0 or 1 performance status
- 4.1.5. Estimated life expectancy > 3 months..
- 4.1.6. Age \geq 18 years, but \leq 75.
- 4.1.7. Adequate hematologic function, with WBC \geq 3000/microliter, hemoglobin \geq 9 g/dL (may transfuse or use erythropoietin to achieve this level), platelets \geq 75,000/microliter; PT-INR <1.5, PTT <1.5X ULN
- 4.1.8. Adequate renal and hepatic function, with serum creatinine < 1.5 mg/dL, bilirubin < 1.5 mg/dL (except for Gilbert's syndrome which will allow bilirubin \leq 2.0 mg/dL), ALT and AST \leq 2.5 x upper limit of normal.
- 4.1.9. Patients who have received prior CEA-targeted immunotherapy are eligible for this trial, if this treatment was discontinued at least 3 months prior to enrollment.
- 4.1.10. Patients who are taking medications that do not have a known history of immunosuppression are eligible for this trial.
- 4.1.11. Ability to understand and provide signed informed consent that fulfills Institutional Review Board's guidelines.
- 4.1.12. Ability to return to Duke University Medical Center for adequate follow-up, as required by this protocol.

4.2. Criteria for Patient Exclusion

- 4.2.1 Patients with concurrent cytotoxic chemotherapy or radiation therapy should be excluded. There are no exclusions based on the number of prior chemotherapy, biologic, hormonal, or experimental regimens. Except for the permitted concomitant therapies (bevacizumab, cetuximab, trastuzumab, erlotinib, gefitinib, or hormonal therapy which patients must have been on for at least 3 months at the time of enrollment if they intend to continue them with the vaccine), there must be at least 3 months between any prior CEA-targeted immunotherapy and study treatment and at least 4 weeks between any other prior therapy (including radiotherapy) and study treatment. Patients must have recovered from all acute toxicities from prior treatment.
- 4.2.2. Patients with a history of brain metastases will not be permitted
- 4.2.3. Patients with a history of autoimmune disease, such as but not restricted to, inflammatory bowel disease, systemic lupus erythematosus, ankylosing spondylitis, scleroderma, or multiple sclerosis. Autoimmune related thyroid disease and vitiligo are permitted.
- 4.2.4. Patients with serious intercurrent chronic or acute illness, such as cardiac disease (NYHA class III or IV), hepatic disease, or other illness considered by the Principal Investigator as unwarranted high risk for investigational drug treatment.
- 4.2.5. Patients with a medical or psychological impediment to probable compliance with the protocol should be excluded.

- 4.2.6. Concurrent (or within the last 5 years) second malignancy other than non-melanoma skin cancer, cervical carcinoma *in situ*, controlled superficial bladder cancer, or other carcinoma in situ that has been treated.
- 4.2.7. Presence of an active acute or chronic infection including: a urinary tract infection, HIV (as determined by ELISA and confirmed by Western Blot) or viral hepatitis (as determined by HBsAg and Hepatitis C serology). Patients with HIV are excluded based on immuno-suppression, which may render them unable to respond to the vaccine; patients with chronic hepatitis are excluded because of concern that hepatitis could be exacerbated by the injections. Patients with active CMV disease will be excluded, but CMV seropositive patients will be eligible.
- 4.2.8. Patients on steroid therapy (or other immuno-suppressives, such as azathioprine or cyclosporin A) are excluded on the basis of potential immune suppression. Patients must have had 6 weeks of discontinuation of any steroid therapy (except that used as pre-medication for chemotherapy or contrast-enhanced studies) prior to enrollment.
- 4.2.9. Patients with allergies to any component of the vaccine will be excluded from the protocol.
- 4.2.10. Pregnant and nursing women should be excluded from the protocol since this research may have unknown and harmful effects on an unborn child or on young children. If the patient is sexually active, the patient must agree to use a medically acceptable form of birth control while receiving treatment and for a period of 4 months following the last vaccination therapy. It is not known whether the treatment used in this study could affect the sperm and could potentially harm a child that may be fathered while on this study.
- 4.2.11. Patients with acute or chronic skin disorders that will interfere with injection into the skin of the extremities or subsequent assessment of potential skin reactions will be excluded.
- 4.2.12. Patients will be allowed warfarin 1mg po qd for port prophylaxis but not full dose warfarin or low molecular weight heparin.

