- 4.2.8. Patients on steroid therapy (or other immuno-suppressives, such as azathioprine or cyclosporin A) are excluded on the basis of potential immune suppression. Patients must have had 6 weeks of discontinuation of any steroid therapy (except that used as pre-medication for chemotherapy or contrast-enhanced studies) prior to enrollment.
- 4.2.9. 4.2.9. Pregnant and nursing women should be excluded from the protocol since this research may have unknown and harmful effects on an unborn child or on young children. If the patient is sexually active, the patient must agree to use a medically acceptable form of birth control while receiving treatment and for a period of 4 months following the last vaccination therapy. It is not known whether the treatment used in this study could affect the sperm and could potentially harm a child that may be fathered while on this study.
- 4.2.10. Patients with acute or chronic skin disorders that will interfere with injection into the skin of the extremities or subsequent assessment of potential skin reactions will be excluded.
- 4.2.11. Patients will be allowed warfarin 1mg po qd other than for port prophylaxis.
- 4.2.12. Patients with metastatic disease which is determined to be resectable will be excluded.

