 - 4.2.9. Pregnant and nursing women should be excluded from the protocol since this research may have unknown and harmful effects on an unborn child or on young children. If the patient is sexually active, the patient must agree to use a medically acceptable form of birth control while receiving treatment and for a period of 4 months following the last vaccination therapy. It is not known whether the treatment used in this study could affect the sperm and could potentially harm a child that may be fathered while on this study.
 - 4.2.10. Patients with acute or chronic skin disorders that will interfere with injection into the skin of the extremities or subsequent assessment of potential skin reactions will be excluded.
 - 4.2.11. Patients will be allowed warfarin 1mg po qd other than for port prophylaxis.
 - 4.2.11. Patients with metastatic disease which is determined to be resectable will be excluded.

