- 4.2.8. Patients on chronic steroid therapy (or other immuno-suppressives, such as azathioprine or cyclosporin A) are excluded on the basis of potential immune suppression. Patients must have had 6 weeks of discontinuation of any steroid therapy (except that used as pre-medication for chemotherapy or contrast-enhanced studies or for acute treatment (<5 days) of intercurrent medical condition such as a gout flare) prior to enrollment.
- 4.2.9. Pregnant and nursing women should be excluded from the protocol since this research may have unknown and harmful effects on an unborn child or on young children. If the patient is sexually active, the patient must agree to use a medically acceptable form of birth control while receiving treatment and for a period of 4 months following the last vaccination therapy. It is not known whether the treatment used in this study could affect the sperm and could potentially harm a child that may be fathered while on this study.
- 4.2.10. Patients with acute or chronic skin disorders that will interfere with injection into the skin of the extremities or subsequent assessment of potential skin reactions will be excluded.

- 4.2.11. Patients with metastatic disease which is determined to be resectable must have been referred to a surgeon for consideration of resection.

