6. TREATMENT PLAN

Patients will be enrolled into successive dosage level cohorts of 3 or 6 patients and monitored for dose-limiting toxicity (DLT).

DLT (Based on NCI CTCAE version 4.0) is defined as any Grade 2, 3 or 4 immediate hypersensitivity reactions, Grade 3 or 4 fever that may possibly be associated with the immunization, Grade ≥ 2 autoimmune events except for vitiligo or fever for less than 2 days and less than 101.5 °F, Grade ≥ 2 allergic reactions (grade 2 is defined as generalized urticaria as defined by CTCAE version 4.0), or Grade ≥ 3 non-hematologic toxicity.

During dose escalation through the first three patients of cohort 3, there will be a minimum of 1 week between enrolling successive patients. The first patient will be called to check on their condition prior to enrolling the second patient since patients can be enrolled after 1 week of initiation of cohort 3. If no DLT have been observed at this point, then further enrollment can occur in cohort 3 and phase II component (Cohort 4) without the 1-week waiting period. Between dosage levels, through Cohort 3, assessment of DLT for dose escalation will be made after all patients in a cohort have had a study visit at least 3 weeks after receiving their first dose of vaccine and all the available safety data and laboratory results have been reviewed. Patients in cohort 5 may begin injections once all patients in cohort 4 have had at least their first injections and all patients in cohort 3 have had a study visit at least 3 weeks after receiving their first dose of vaccine. If DLT occurs in $<33\%$ of patients in a given dosage level cohort, progression to the next dosage level will proceed. If DLT occurs in $\geq 33\%$ of patients in a given cohort, the next lower dosage level will be defined as the maximum tolerated dose (MTD). If DLT occurs in $<33\%$ of patients in the highest dosage level tested, that dosage level will be defined as the MTD. In phase II (Cohort 4) and Cohort 5, if at any time the rate of DLT in patients enrolled is $\geq 33\%$, the MTD will be re-defined as the next lower dosage level. Additional details of this dose escalation and de-escalation plan are provided below and in Figures 3A, 3B and Table 3.

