- 6) Cohort 6: Up to ten (10) patients will receive Ad5 [E1-, E2b-]-CEA(6D) at a dose of 5×10^{11} particles SQ in 1.0 mL every 3 weeks for 3 immunizations. Patients will be permitted to receive booster doses of Ad5 [E1-, E2b-]-CEA(6D) every 3 months for a period of two years following the first 3 treatments. In the event that a qualified patient undergoes reimaging prior to the completion of their initial 3 study immunizations and is found to have disease progression, the patient should continue on the immunization protocol because this could be a “flare reaction” associated with the vaccine which may be an inflammatory response. Patients will be required to have MRI/CT scans performed prior to initiation of treatment, at 3 month intervals +/- 1 month for 12 months or if the investigator believes signs or symptoms are suggestive of progression or relapse. All patients will be followed for overall survival for a period of 24 months from initiation of treatment.
- 7) Patients will have 90 mL peripheral blood drawn prior to each immunization and approximately 3 weeks after the third immunization (Week 9) to determine whether there is an effect on the immune response at specific time points during the study and/or after a specific number of immunizations.
- 8) Time to progression will be measured using CT scans performed at approximately 3 month intervals (based on clinical standard of care).
- 9) For all patients, if scheduling conflicts arise, the scheduled 3-week interval between immunizations may be modified so that the interval between immunizations is between 20 and 28 days (3 weeks -1 day to 3 weeks +7 days). If the second and/or third immunization is delayed, the subsequent immunizations should occur no earlier than 20 days after the previous immunization.
- 10) The following safety events will trigger a temporary suspension of study vaccinations:
 - a) If one or more patients develop a Grade 4 allergic reaction without a clear attributable cause, other than study vaccine
 - b) Death not attributed to disease.

Assessment of these halting rules is a review of cumulative events for all study participants, and should not be confused with reasons for delaying or terminating the immunization schedule of any individual patient.

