7.3.3 Treatment of Toxicity

For acute allergic reactions, use of diphenhydramine 25-50 mg IV, corticosteroids (Solumedrol 100 mg), and epinephrine (1:1000, 0.3-1 mL sq) should be considered. These medications are available in the clinical setting where the vaccine will be administered. For auto-immunity, corticosteroids (prednisone 0.5-1 mg/kg/d) should be considered. Clinical assessment of other targets, such as thyroid, arthritis, urticaria, or proteinuria, for auto-immunity and serum sickness like antigen-antibody complex disease, will also be performed as indicated.

7.3.4 Active Immunotherapy will be Discontinued for:

- 7.3.4.1 Life-threatening anaphylactic reactions related to active immunotherapy
- 7.3.4.2 DLT related to active immunotherapy
- 7.3.4.3 Disease progression (by RECIST criteria). Patients will be offered referral to a medical oncologist for discussion of other treatment options, and for continued medical care.
 - 7.3.4.3.1 Disease progression prior to completing the 3 study immunizations:

In the event that a patient undergoes reimaging studies prior to the completion of their 3 study immunizations and is found to have disease progression, they will be permitted to continue on the study as long as the progression has been 50% or less by RECIST criteria.

If a patient is removed from the study prior to completion of the assigned vaccine schedule for any reason other than toxicity, that patient will be replaced, in order to obtain data to help determine the toxicity of the immunizations. We will allow up to 3 replacements per cohort (Phase I, Dose levels 1 and 2; Phase II, MTD).

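### The current exclusion list no longer names known allergy to a vaccine component, and the documents give no reason for dropping it, although allergic reactions still count as DLT and can suspend dosing

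*Combined protocol and SAP*

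**What the plan says.** The file holds seven successive full versions of the protocol. In the first two, Section 4.2 (Criteria for Patient Exclusion) has as item 4.2.9: "Patients with allergies to any component of the vaccine will be excluded from the protocol". In the third version that sentence is gone, and its place is taken by the pregnancy criterion, printed with a doubled number: "4.2.9. 4.2.9. Pregnant and nursing women should be excluded from the protocol". In the remaining versions, including the last, the item reads "4.2.9. Pregnant and nursing women should be excluded from the protocol".

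The last version still deals with allergic reactions in several places:

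- The Protocol Summary lists anaphylaxis first among the potential risks.
- Section 6 (Treatment Plan) says that DLT "is defined as any Grade 2, 3 or 4 immediate hypersensitivity reactions", and it adds Grade 2 or higher "allergic reactions (grade 2 is defined as generalized urticaria as defined by CTCAE version 4.0").
- Section 6, item 10, suspends study vaccinations temporarily: "If one or more patients develop a Grade 4 allergic reaction without a clear attributable cause, other than study vaccine".
- Section 6.1 stops the study after a possibly related death, or after related Grade 4 toxicity in two patients.
- Section 7.3.4 ends an individual's immunotherapy for "Life-threatening anaphylactic reactions related to active immunotherapy" and for related DLT.

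**The concern.** As the last version is written, no criterion keeps out a patient with a known allergy to a component of the product. If such a patient is enrolled and reacts, the event is a genuine, related DLT. It is also a foreseeable one, in a patient whom the sponsor at first chose not to treat. Two things are at stake. The first is the safety of that patient. The second is the interpretation of the primary safety endpoint, because the reaction counts towards the DLT thresholds and, if it is Grade 4, can suspend dosing for everyone.

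**Working it through.** **Is the criterion really absent from the current text?**

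| Version in the file | Item 4.2.9 | Component-allergy exclusion |
|---|---|---|
| 1 and 2 | Allergy to a vaccine component | Present |
| 3 | Pregnancy and nursing (number doubled) | Absent |
| 4 to 7 | Pregnancy and nursing | Absent |

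It is present in 2 of 7 versions and absent from 5 of 7. In the last version it appears in no other item of 4.1 or 4.2. The pages removed from the public file do not fall inside any Section 4.2, so redaction does not explain the gap. The comparison is between full protocol texts, and the gap is in the operative one.

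**Does another criterion cover it?** Item 4.2.4 lets the investigator exclude for other illness judged to carry unwarranted high risk. It is discretionary, it speaks of illness, and it does not name allergy. The same clause stood beside the separate allergy item in versions 1 and 2, so the authors did not then rely on it for this purpose.

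**How large is the effect on a dose decision?** The plan gives no figure to reproduce. The decision that can be calculated is the six-patient rule (Section 6, cohorts 3 and 5), under which two DLT reject the level.

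Inputs:

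- Cohort size 6 and threshold 2, from Section 6.
- DLT rate in non-allergic patients, p = 10% (assumed; 5% and 20% also shown).
- Proportion of enrolled patients with a known component allergy, q = 0.5% to 2% (assumed; not in the documents).
- DLT certain in an allergic patient (assumed; this makes the results upper bounds for a given p and q).

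Step 1, without allergic patients: P(2 or more of 6) = 1 − (1 − p)^6 − 6p(1 − p)^5. At p = 0.10 this is 1 − 0.5314 − 0.3543 = 0.114.

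Step 2, overall DLT rate per patient: p* = p(1 − q) + q. At p = 0.10 this is 0.0995 + 0.005 = 0.1045 for q = 0.5%, and 0.098 + 0.02 = 0.118 for q = 2%.

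Step 3, put p* into the formula of step 1:

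| p | No allergic patients | q = 0.5% | q = 2% |
|---|---|---|---|
| 5% | 3.3% | 3.9% | 5.9% |
| 10% | 11.4% | 12.3% | 15.1% |
| 20% | 34.5% | 35.5% | 38.4% |

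At p = 10% the rise is about 1 to 4 percentage points.

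**How likely is it that such a patient is enrolled at all?** The chance of at least one among n patients is 1 − (1 − q)^n. For the 40 patients of all six cohorts (3 + 3 + 6 + 12 + 6 + 10) it is 18% at q = 0.5% and 55% at q = 2%. For the 10 patients of cohort 6 alone it is 5% and 18%. The smaller figures are the relevant ones if only cohort 6 was still to enrol under the last version. That is an assumption, although the sixth version already reports the MTD as determined.

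**The case against.** The strongest reply is that the last version does not contradict itself. Rules for DLT and for suspension are needed for unforeseen reactions whether or not known allergy is excluded. The evidence of a gap is therefore a difference from superseded text, and the removal may have been deliberate. From version 2 to version 3 the later items each move up by one number, which fits a deliberate deletion with renumbering, and the same amendment reworded other items of 4.2. The visible text describes the vehicle only as saline or formulation buffer and lists no excipients, so whether any candidate could have a known component allergy cannot be judged. Safeguards also remain: history and a criteria review at screening (Section 5), about 30 minutes of observation after each injection (7.1.1), and allergy medication on hand (7.3.3).

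Much of this stands. It rules out three stronger readings that a reader might infer:

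- *That the pregnancy item overwrote the allergy item by accident.* The doubled number is compatible with a slip, but also with list numbering or text extraction. The documents do not show intent.
- *That the chance of rejecting a dose rises from 11% to 41%.* The 41% is 1 − 0.9^5. It supposes that an allergic patient is already in the cohort and is certain to have a DLT, so it leaves out how rarely such a patient would be enrolled.
- *That any allergic reaction halts the trial.* Only a Grade 4 reaction with no clear cause other than the vaccine suspends vaccinations, and the suspension is temporary. Grade 2 and 3 reactions stop the individual as related DLT and count towards the 33% rule.

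Nor did the Summary lose anything, since its criteria did not contain the allergy item in versions 1 and 2 either.

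What the reply does not supply is a reason for the removal, or a current criterion that does the same work. The remaining safeguards detect or treat a reaction, or depend on an investigator choosing to stretch 4.2.4.

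**Conclusion.** The point holds as a gap in the current eligibility criteria. Known allergy to a vaccine component is no longer named as an exclusion, the removal is unexplained, and the rules that act on allergic reactions are still in force. The effect on dose decisions is small: 11.4% becomes 12.3% to 15.1% under the assumed 0.5% to 2% prevalence, a certain DLT in allergic patients and a 10% DLT rate in the others. None of these three inputs comes from the documents. The weight of the point lies in the individual patient, for whom a foreseeable reaction could be avoided by a question at screening. Whether the removal was an error or a decision cannot be settled from the file.

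**What to change.** Reconcile Section 4.2 of the current version with versions 1 and 2 and with the DLT and suspension rules of Section 6. There are two ways to do this: reinstate the sponsor's own sentence as a separately numbered item in 4.2, or state in the protocol or amendment record why it was removed. If it is reinstated, it may also go into the Summary's criteria, as an addition rather than a restoration. The cost is one sentence. The check uses the history and criteria review already done at screening, with at most a very few extra screen failures. No dose, schedule, DLT definition or stopping rule changes.
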